The Intracoronary Stenting and Antithrombotic Regimen–Rapid Early Action for Coronary Treatment (ISAR-REACT) study reported that pretreatment with 600 mg clopidogrel provides outcomes similar to those achieved with a strategy of pretreatment with the addition of abciximab [1] However, an important consideration in the decision for pretreatment is the associated risk of bleeding in those patients requiring coronary bypass surgery. The Clopidogrel Loading with Eptifibatide to Arrest the Reactivity of Platelets (CLEAR PLATELETS study) [2] showed that the administration of eptifibatide with either a 300 mg or 600 mg of clopidogrel provides the most sustained platelet inhibition and was associated with the lowest incidence of myonecrosis compared with those who received clopidogrel alone. The incremental increase in myonecrosis observed in patients with higher levels of post-treatment platelet reactivity lend strong support to the concept that activated platelets during PCI play a central role in the mediation of post-stent myonecrosis. However, the findings of ISAR-REACT trial is not relevant when physicians decide not to pretreat patients whose coronary anatomy is unknown before the stenting.

Since stenting and the use of thienopyridines have become routine, there has been a decrease in the incidence of acute closure, but because of concern with respect to bleeding complications after PCI, adopting a bolus injection or brief infusion of glycoprotein inhibitors (GPI) has reduced such complications. In this respect, Kini et al [3] demonstrated that among patients undergoing PCI, GPI bolus only reduced vascular/bleeding complications with similar MACE and reduced cost when compared with GPI bolus plus continuous infusion. In addition, GPI bolus only improved ambulatory PCI and reduced length of stay. Marmur et al. [4] compared long-term mortality after bolus only administration of abciximab, eptifibatide, and tirofiban during PCI and demonstrated that eptifibatide, when given as bolus-only during PCI, improved the long-term survival compared to abciximab. Furthermore, Fung et al. [5] demonstrated that in patients undergoing non-emergent PCI, the post-procedural infusion of eptifibatide can be abbreviated to <2 h and that was not inferior to 18-h infusion in preventing ischemic events. Furthermore, they concluded that the abbreviated infusion of eptifibatide reduced both cost and post-procedural major bleeding.

We recently randomized 70 patients with Non-ST-Segment Myocardial Infarction (NSTEMI) to ticagrelor 190 mg loading and eptifibatide bolus-only (TEP) vs. ticagrelor loading and eptifibatide bolus plus 2 h infusion (TEPI) administered before stenting [Fig. 1]. Light transmission aggregometry was performed and percent inhibition of platelet aggregation (%IPA) was calculated at baseline, and at 2, 6, and 24 h using ADP, TRAP, collagen, and arachidonic acid (AA). Cardiac enzymes, hemoglobin and hematocrit were measured at baseline and at 24 h. The event rates were determined at 30-day follow-up. We demonstrated that in patients randomized to TEP vs. TEPI, there were no significant difference in the %IPA values at 2 h and 6 h with ADP 5 μ M ($100\% \pm 0.01$ vs. $99\% \pm 0.25$ and $99\% \pm 2.4$ vs. $99\% \pm 1.2$, respectively) and with ADP 20 μ M as well as with collagen. However, %IPA was lower at 24 h (still >60% platelet inhibition) compared with that at 2 h and 6 h. Percent IPA with TRAP 10 or 20 μ M was higher at 6 h in patients randomized to

TEPI vs. TEP ($87\% \pm 13$ vs. $74\% \pm 17$; $P < 0.01$, respectively), but this had no bearing on outcomes since ADP was highly inhibited by ticagrelor at 6 h. There were no significant differences in troponin or hemoglobin levels among the groups. During follow-up, and there was no stent thrombosis or myocardial infarction.

We concluded that %IPA values with ADP and collagen were not significantly different comparing ticagrelor with eptifibatide bolus only vs. ticagrelor and eptifibatide bolus plus 2 h infusion. Eptifibatide bolus only highly inhibited platelets aggregation while allowing bridging to the antiplatelet effect of ticagrelor and circumventing the need for continuous eptifibatide infusion. There was no significant difference in bleeding or MI between the 2 groups.

RATIONALE

The antiplatelet effect of clopidogrel is slow in onset, variable, and irreversible; approximately 15 to 30% of patients are non-responsive [6]. Furthermore, a 75-mg/d clopidogrel maintenance dose requires at least 5 days, and a 600-mg loading dose of clopidogrel requires up to 8 hours to achieve a 50% steady state of inhibition of ADP-induced platelet aggregation [7-9]. The difference in the clinical effects of ticagrelor compared with clopidogrel lies in the fact that ticagrelor exerts more rapid, more potent, and more consistent inhibition of platelets [10,11]. In the CLEAR

PLATELETS study [2], administration of eptifibatide with either a 300 mg or 600 mg of clopidogrel provided the most sustained platelet inhibition and was associated with the lowest incidence of myonecrosis compared with 600 mg loading dose of clopidogrel administered in the cath lab . The Platelet Inhibition and Patient Outcomes (PLATO) trial [12] demonstrated that dual antiplatelet therapy with aspirin and ticagrelor was superior to aspirin and clopidogrel in reducing thrombotic complications in patients with acute coronary syndrome undergoing PCI. Glycoprotein IIb/IIIa inhibitors (GPI) bolus and infusion was used with ticagrelor in 40% of patients in the PLATO trial. However, GPI use was not randomized and the benefit of which cannot be substantiated. On the other hand, the CLEAR PLATELET study showed clopidogrel and eptifibatide bolus and infusion was associated with reduced myonecrosis. In addition, they showed that platelet inhibition was significantly higher with 600 mg vs. 300 mg of clopidogrel. In the Ad Hoc PCI study, ticagrelor or clopidogrel was administered before PCI in patients with unstable angina and there was a significant reduction in the PRU level with ticagrelor as compared with clopidogrel. We demonstrated that %IPA with ticagrelor and eptifibatide bolus was not significantly different than ticagrelor and eptifibatide bolus and short infusion.

The inhibition of platelets is significantly faster and stronger with Ticagrelor than clopidogrel. We hypothesized that inhibition of platelet aggregation with ticagrelor alone will be non-inferior to that of clopidogrel and eptifibatide bolus. The present study will be the first to investigate the pharmacodynamic effects of ticagrelor vs. clopidogrel plus eptifibatide bolus in patients undergoing elective PCI in patients with troponin negative unstable angina or stable angina. If ticagrelor alone is indeed non-inferior to clopidogrel and eptifibatide bolus, this will pave the way for a large randomized study to demonstrate the safety and efficacy of ticagrelor alone as compared with concomitant administration of clopidogrel and eptifibatide.

Study Hypothesis: To compare the percent inhibition of platelet aggregation with ticagrelor compared with clopidogrel and eptifibatide bolus in patients with stable angina or in patients with troponin-negative unstable angina.

Inclusion Criteria:

[figure not shown]
Patients with stable angina with evidence for at least >10% perfusion defect (moderate to large ischemia) or patients with troponin-negative unstable angina.

Exclusion Criteria: A need for oral anticoagulation therapy; an increased risk of bradycardia, and concomitant therapy with a strong cytochrome P-450 inhibitors; surgery<4 weeks; The use of any thienopyridines prior to randomization; upstream use of GP IIb/IIIa inhibitors; bleeding diathesis or major bleeding episode within 2 weeks; thrombocytopenia; incessant chest pain; hemodynamic instability; NSTEMI as evidenced by elevation of troponin levels; renal failure with a serum creatinine >2.0 mg/dL; and anemia with HCT<30%.

Methods

In this study, 100 patients with stable angina or troponin negative unstable angina, will be randomized to ticagrelor loading dose versus clopidogrel loading dose and eptifibatide bolus only administrated before PCI. Platelet function testing will be performed at baseline, at 30 min post-loading dose, 2 h, and 4 h, and 24 h. All patients will be started on aspirin 81 mg prior to procedure . Heparin 60 units/kg will be administered intravenously before PCI. PCI will be performed in accordance with standard clinical practice. Please see Fig. 2, Design of the study below and Table 1.

Fig. 2

Blood Sampling for Platelet Function Testing

Blood will be collected from an antecubital vein into vacutainer tubes (Becton-Dickinson, Franklin Lakes, NJ) that contain 3.2% trisodium citrate for light-transmittance aggregometry. All measurements will be performed at the UAB thrombosis research laboratory.

Light-Transmittance Aggregometry

Platelet aggregation induced by ADP (5 and 20 μm), TRAP (10 and 20 μm) platelet-rich plasma will be measured with a Chronolog Optical Aggregometer (model 490-4D; Chronolog Corporation, Havertown, Pa). The final extent of aggregation, measured at 6 minutes after agonist addition, and the maximal extent of aggregation will be expressed as the percent change in light transmittance from baseline with platelet-poor plasma as a reference. Inhibition of platelet aggregation (IPA) will be calculated as follows:

$$\text{IPA}(\%) = 100\% \times \frac{\text{PA}_t - \text{PA}_b}{\text{PA}_b}$$

Where PA is platelet aggregation, b is predosing, and t is postdosing.

Statistical Analysis

The present study is an exploratory trial to investigate the percent inhibition of platelet activity (%IPA) (measured by light-transmittance aggregometry) comparing the loading dose of ticagrelor

with loading dose of clopidogrel and 2 boluses of eptifibatide measured at all time-points. Since there are no preliminary data available, no power calculation was performed. Statistical analysis will be performed using the Statistical Package for Social Sciences, version 22.0, software package for Windows (SPSS, Inc., Chicago, Illinois). Data will be presented as mean \pm 1 SD or frequencies; a value of $P < 0.05$ will be considered statistically significant. %IPA of ticagrelor and 2 boluses of eptifibatide vs. loading dose of clopidogrel and 2 boluses of eptifibatide will be compared at all time-points using repeated measures ANOVA. Continuous variables will be compared between the 2 treatment groups with Student t test. For comparisons of categorical data, the Chi-Square test will be performed.

End-Points

The primary end point of the study is to compare %IPA induced by ADP at 2 h, in patients randomized to the loading dose of ticagrelor with loading dose of clopidogrel and 2 boluses of eptifibatide measured at 2 h post loading dose. Secondary endpoints of the study are to compare %IPA induced by ADP and TRAP in patients randomized to the loading dose of ticagrelor with loading dose of clopidogrel and 2 boluses of eptifibatide at all time-points. Other secondary outcomes include: 1) the occurrence of post-procedural myonecrosis comparing the 2 groups. Ischemic myonecrosis will be defined as elevated post-procedure troponin-1 level $>0.26 \mu\text{g/l}$; and 2) the rate minor (a fall in hemoglobin of 3 to $<5 \text{ g/dL}$) and major bleeding (a fall in the hemoglobin $>5 \text{ g/dL}$) between the groups.

Anticipated Findings

Since platelet inhibition with ticagrelor starts rapidly, we expect that %IPA at 2 h will be no significantly different than clopidogrel and eptifibatide bolus. In addition, since eptifibatide half-life is short, we expect that %IPA at 24 h will be higher with ticagrelor than clopidogrel and eptifibatide bolus.

We anticipate the results of the present study will set the stage for a large randomized trial comparing myonecrosis, stent thrombosis, death, myocardial infarction, bleeding, and costs in patients randomized to ticagrelor only vs. loading dose of clopidogrel and 2 boluses of eptifibatide.

Table 1: Schedule of treatment

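### The Rationale hypothesises non-inferiority, but the analysis has only difference tests and no margin or confidence-interval criterion

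*Combined protocol and SAP*

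**What the plan says.** The Rationale gives the hypothesis: "We hypothesized that inhibition of platelet aggregation with ticagrelor alone will be non-inferior to that of clopidogrel and eptifibatide bolus". It then attaches a use to it: "If ticagrelor alone is indeed non-inferior to clopidogrel and eptifibatide bolus, this will pave the way for a large randomized study". The line labelled Study Hypothesis that follows is neutral and speaks only of a comparison, as does the primary endpoint in End-Points (ADP-induced %IPA at 2 h).

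The Statistical Analysis section assigns %IPA to repeated measures ANOVA across the time-points and adds: "Continuous variables will be compared between the 2 treatment groups with Student t test". The decision threshold is "a value of $P < 0.05$ will be considered statistically significant". Data are to be shown as mean ± 1 SD. The section calls the trial exploratory and says: "Since there are no preliminary data available, no power calculation was performed".

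For the primary time-point, Anticipated Findings states: "we expect that %IPA at 2 h will be no significantly different than clopidogrel and eptifibatide bolus".

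Neither a non-inferiority margin, nor a confidence interval, nor a non-inferiority or equivalence test is mentioned anywhere.

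**The concern.** A difference test asks whether the data are incompatible with no difference. A non-significant answer does not exclude a ticagrelor deficit large enough to matter. To support non-inferiority, the interval for the difference must exclude deficits beyond a stated margin.

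The result the sponsor expects at 2 h is therefore one that the plan cannot turn into the claim it wants to make. The plan does not say that P ≥ 0.05 will be read as non-inferiority, but it offers no other criterion, and the Rationale already summarises the earlier 70-patient study by the absence of a significant difference. At stake is whether the non-inferiority statement offered in support of a large trial has an evidential basis.

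**Working it through.** **Logic.** This part needs no numbers.

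- Hypothesis (Rationale): ticagrelor alone is not worse than clopidogrel plus eptifibatide by more than some amount. The amount is not stated.
- Test (Statistical Analysis): the null hypothesis is zero difference, with significance at 0.05.
- Expected outcome (Anticipated Findings): the null is not rejected at 2 h.
- Failing to reject zero difference says nothing about an unstated margin. Only a significant result in ticagrelor's favour would support the hypothesis under the planned tests.

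**Size.** This part is illustrative. The plan has no power figure to reproduce, because no power calculation was done.

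Inputs:

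- Total of 100 patients (Methods). A 1:1 split, 50 per arm, is assumed.
- Two-sided 0.05 is assumed, since sidedness is not stated.
- No SD is given for 2-h ADP %IPA under either regimen. The earlier study, described before the Rationale, gives ADP 5 µM SDs of 0.01 and 0.25 at 2 h and 2.4 and 1.2 at 6 h. Those come from NSTEMI patients who all received ticagrelor plus eptifibatide. Its TRAP SDs at 6 h are 13 and 17. SDs of 20 and 30 are added as assumptions with no source in the documents.
- A true deficit of 10 %IPA points is assumed, with higher %IPA meaning more inhibition.

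Formulas:

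- SE = √[(SD₁² + SD₂²)/50]
- 95% half-width = 1.984 × SE (t with 98 df)
- Largest deficit still inside the interval when the result is just non-significant with ticagrelor lower = 2 × half-width
- P(non-significant) from the noncentral t, 98 df, noncentrality 10/SE

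Example, SD 17 in both arms: SE = √[(289 + 289)/50] = 3.40; half-width = 1.984 × 3.40 = 6.75; twice that = 13.5.

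| SD ticagrelor / comparator | SE | Half-width | Deficit left in interval | P(non-sig., true deficit 10) |
|---|---|---|---|---|
| 13 / 13 | 2.60 | 5.16 | 10.3 | 3% |
| 17 / 17 | 3.40 | 6.75 | 13.5 | 17% |
| 20 / 20 | 4.00 | 7.94 | 15.9 | 30% |
| 30 / 30 | 6.00 | 11.91 | 23.8 | 62% |
| 13 / 2.4 | 1.87 | 3.71 | 7.4 | about 0% |
| 17 / 2.4 | 2.43 | 4.82 | 9.6 | 2% |
| 20 / 2.4 | 2.85 | 5.65 | 11.3 | 7% |
| 30 / 2.4 | 4.26 | 8.45 | 16.9 | 36% |

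The lower block represents a comparator near its ceiling. With SD 2.4 in both arms, SE = 0.48, the half-width is 0.95 and a non-significant result leaves at most 1.9 points. In that case the P value fails in the other direction: a true 2-point deficit would be significant about 98% of the time, and the test would not say whether 2 points matter.

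The arithmetic uses the t test at 2 h. The plan does not say whether the t test or the ANOVA governs the primary comparison, but both are difference tests.

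**The case against.** The strongest reply is that non-inferiority is only narrative here. The labelled hypothesis and the primary endpoint are neutral, the trial is exploratory, and its consequence is another randomised trial, not a change in practice. The closing sentence of Anticipated Findings foresees that large trial with no non-inferiority condition. Group means and SDs will be reported, so a reader could compute an approximate interval. This stands as a reason to treat the point as a modest, cheap repair. It does not supply a criterion for the hypothesis that the Rationale states and puts to use.

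The size is also open to challenge. The SDs of 13 and 17 belong to another agonist and time-point, and 20 and 30 have no source. %IPA is capped at 100, so an SD of 30 near that ceiling would mean skewed data, for which normal-theory figures are least credible. That is right: the size is undetermined, and the table shows only a range.

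The small ADP SDs in the earlier study might seem to settle the matter, but they are a weak basis for reassurance. Taking 35 per arm (70 split evenly, an assumption), the printed 2-h values of 100 ± 0.01 and 99 ± 0.25 give SE = √[(0.01² + 0.25²)/35] = 0.042 and t = 1/0.042 ≈ 24, yet the difference is reported as non-significant. Rounded means or mislabelled spreads could explain this. In any case the regimens and patients differ from those in this trial.

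**Conclusion.** The concern holds. The mismatch between a non-inferiority hypothesis and an analysis that contains only difference tests is plain from the text and does not depend on any assumed SD. Its practical size cannot be fixed from the documents. It is negligible if both arms have an SD near 2.4. It is substantial at a common SD of 20 to 30, where a true 10-point deficit would be missed 30% to 62% of the time with an assumed 50 per arm. Because the trial is exploratory, this should be fixed but does not undermine the design.

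**What to change.** Make the primary result the 2-h difference in ADP-induced %IPA (ticagrelor minus clopidogrel plus eptifibatide) with its two-sided 95% CI, and state that P ≥ 0.05 will not be read as non-inferiority. Then choose one of two options.

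- **(a)** Drop the non-inferiority wording from the Rationale and present the result as an exploratory estimate with its interval. The cost is a wording change and one interval, with no added patients.
- **(b)** Before analysis, prespecify and justify a margin in %IPA points, and claim non-inferiority only if the lower 95% limit lies above minus that margin. Acknowledge that 100 patients may be too few.

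For option (b), power with 50 per arm and no true difference, at illustrative margins, is:

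| Ticagrelor SD | Margin 10, equal SDs | Margin 10, comparator SD 2.4 | Margin 5, equal SDs | Margin 5, comparator SD 2.4 |
|---|---|---|---|---|
| 13 | 97% | >99% | 48% | 75% |
| 17 | 83% | 98% | 31% | 53% |
| 20 | 70% | 93% | 24% | 41% |
| 30 | 38% | 64% | 13% | 21% |

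For 80% power at the 10-point margin, the numbers per arm are 28/47/64/143 with equal SDs and about 16/26/34/74 with comparator SD 2.4.

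Three secondary repairs would give the interval a clear direction and target; the finding does not rest on them.

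- The IPA formula under Light-Transmittance Aggregometry makes inhibition negative, whereas the earlier study's values are near +99%. Write it as 100 × (PA_b − PA_t)/PA_b.
- Name one ADP concentration and one aggregation measure (final or maximal) as primary.
- The ANOVA sentence in Statistical Analysis puts eptifibatide in the ticagrelor arm, unlike the Rationale, Methods and End-Points. These must be reconciled.

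The downside of either option is that the resulting claim may be less favourable.

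### The only formula for the primary variable, %IPA, has its sign reversed: complete inhibition comes out as -100%, and a higher value means less inhibition

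*Combined protocol and SAP*

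**What the plan says.** The Light-Transmittance Aggregometry section introduces the measure with "Inhibition of platelet aggregation (IPA) will be calculated as follows" and prints

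IPA(%) = 100% × (`PA_t` − `PA_b`) / `PA_b`.

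The legend reads "Where PA is platelet aggregation, b is predosing, and t is postdosing". No other formula for %IPA appears, and there is no absolute-value rule or stated sign convention.

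The variable carries the main comparison. Under End-Points, "The primary end point of the study is to compare %IPA induced by ADP at 2 h", and the secondary endpoints use %IPA with ADP and TRAP at all time-points.

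Three other places bear on direction:

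- Anticipated Findings, on this trial: "we expect that %IPA at 24 h will be higher with ticagrelor than clopidogrel and eptifibatide bolus". The reason given is that eptifibatide has a short half-life.
- Rationale: "We hypothesized that inhibition of platelet aggregation with ticagrelor alone will be non-inferior to that of clopidogrel and eptifibatide bolus".
- The introductory account of the team's earlier randomised study in 70 NSTEMI patients reports %IPA of 99% to 100% with ADP 5 μM at 2 h and 6 h. It then says that %"IPA was lower at 24 h (still >60% platelet inhibition) compared with that at 2 h and 6 h".

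**The concern.** The quantity is named inhibition, but the expression increases as aggregation increases. A drug that abolishes aggregation scores −100%, and a patient whose aggregation rises after dosing gets a positive score. This conflicts with the name of the measure and with the 24 h expectation. That expectation rests on the comparator's effect wearing off, so a higher %IPA there can only mean more inhibition.

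This is an instruction for computing the primary variable. An analyst who follows it literally will report means and between-arm differences with the wrong sign. A 24 h result in ticagrelor's favour would appear as a lower %IPA and would seem to refute the stated expectation. The hypothesis in the Rationale is also directional: if it is judged on this variable, the arm that looks worse is the one with more inhibition.

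**Working it through.** **Inputs.** The formula and its legend come from Light-Transmittance Aggregometry. The total of 100 randomised patients comes from Methods; I assume 50 per arm. The documents give no aggregation values or SDs for this trial, so the baseline of 70%, the 24 h means and the SDs below are assumptions. The plan gives no power calculation or other figure that depends on the formula, so there is no stated number to reproduce.

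**1. Algebra.** (`PA_t` − `PA_b`)/`PA_b` = −(`PA_b` − `PA_t`)/`PA_b`. The printed expression is therefore exactly minus the percent inhibition, whatever the data. The legend does not rescue it, because b is predose and t is postdose.

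**2. Substitution at an assumed baseline of 70.** The result depends only on the ratio `PA_t`/`PA_b`.

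| Postdose aggregation | As printed, 100(t − b)/b | Numerator reversed, 100(b − t)/b |
|---|---|---|
| 0 (complete inhibition) | −100 | 100 |
| 0.7 | −99 | 99 |
| 7 | −90 | 90 |
| 28 | −60 | 60 |
| 70 (no change) | 0 | 0 |
| 77 (rise of 10%) | +10 | −10 |

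**3. Comparison with the earlier study's scale.** To obtain a value v from the printed formula, `PA_t`/`PA_b` must equal 1 + v/100. Values of 100, 99 and 60 would need postdose aggregation of 2.00, 1.99 and 1.60 times baseline, which is a rise after antiplatelet loading. With the numerator reversed the ratio is 1 − v/100, giving 0, 0.01 and 0.40, which is what strong inhibition looks like. The earlier study's own formula is not given, so this shows only the scale the authors have in mind.

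**4. Effect on a between-arm comparison.** Assume true inhibition at 24 h of 80% with ticagrelor and 60% with clopidogrel plus eptifibatide, a common SD of 20 and 50 per arm.

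- Standard error = 20 × √(2/50) = 20 × 0.2 = 4.
- As printed: means −80 and −60, difference −20, t = −20/4 = −5.00.
- Numerator reversed: means 80 and 60, difference +20, t = 20/4 = +5.00.
- Two-sided P on 98 degrees of freedom is 2.5 × 10⁻⁶ in both cases.

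Over a range of SDs:

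| Assumed SD | t as printed | t reversed | Two-sided P, both formulas |
|---|---|---|---|
| 10 | −10.0 | +10.0 | 1.2 × 10⁻¹⁶ |
| 20 | −5.00 | +5.00 | 2.5 × 10⁻⁶ |
| 30 | −3.33 | +3.33 | 0.0012 |

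**5. Repeated measures ANOVA.** F statistics are ratios of mean squares and do not change when every value is multiplied by −1. One simulated data set (assumed values, 2 × 50 patients, four postdose times) gave identical F values under both formulas: 4.51 for arm, 61.7 for time and 227.9 for arm by time.

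**The case against.** The best case for leaving this alone is that no planned test result changes. The statistical section says "Continuous variables will be compared between the 2 treatment groups with Student t test", with repeated measures ANOVA across time-points, and both give the same two-sided P-value either way. The trial is described as exploratory. The 2 h expectation is of no significant difference and has no direction, and no margin, confidence limit or responder cut-off uses the sign. The label and the positive values quoted from the earlier study make the intended orientation clear, and a table of values near −100% headed inhibition would soon be noticed. The hypothesis in the Rationale speaks of inhibition as a concept, not of a signed %IPA value. Finally, the error lies in the order of two subscripted terms and could be a typesetting slip.

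Most of this is right about consequences, and it limits the severity. It does not remove the error. A protocol formula exists so that the analyst need not infer what was meant, and this one instructs the opposite of its own label. Reading it as an absolute value would not be safe, because a 10% rise in aggregation would then count as 10% inhibition. If some values were computed from the printed formula and others on the positive scale, the harmless uniform change of sign would be lost. On the Rationale, it is fair that no non-inferiority analysis is specified, so the point is about how the result would be read and not about a test that would fail. As for a slip, the equation is complete and agrees with its legend. A slip at the drafting stage would in any case need the same correction.

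**Conclusion.** The concern holds. The printed definition of %IPA is the negative of inhibition. It contradicts its own name and the 24 h expectation for this trial, and nothing else in the documents reconciles them. The reversal follows from algebra alone and needs no assumed data; the assumed values above serve only to illustrate its size.

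The consequence is confined to sign and interpretation. A true 20-point advantage for ticagrelor at 24 h would be reported as a difference of −20, and the expectation and hypothesis would be read backwards if judged on that variable. Invariance of the tests assumes that the same formula is applied to every value and that tests are two-sided; the plan sets P < 0.05 without stating sidedness. This should be corrected before analysis because it defines the primary variable, but it does not threaten the validity of the planned comparisons.

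**What to change.** Replace the formula with IPA(%) = 100% × (`PA_b` − `PA_t`)/`PA_b`. Add a sentence saying that larger values mean more inhibition and that a negative value, meaning aggregation above baseline, is kept as negative. Confirm that %IPA is computed this way for every agonist and time-point in the analysis.

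The cost is one line in the protocol. Sample size, sampling times, assays and planned tests do not change.

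### Does the ANOVA sentence that gives eptifibatide to both arms change which comparison the trial will make?

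*Combined protocol and SAP*

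**What the plan says.** The hypothesis in the Rationale section is explicit about the arms: "We hypothesized that inhibition of platelet aggregation with ticagrelor alone will be non-inferior to that of clopidogrel and eptifibatide bolus". The Methods section says that 100 patients "will be randomized to ticagrelor loading dose versus clopidogrel loading dose and eptifibatide bolus only administrated before PCI".

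The Statistical Analysis section opens with the same pairing, "measured by light-transmittance aggregometry) comparing the loading dose of ticagrelor" on one side and clopidogrel with two eptifibatide boluses on the other. A few lines later, the sentence that names a method for %IPA reads "IPA of ticagrelor and 2 boluses of eptifibatide vs. loading dose of clopidogrel and 2 boluses of eptifibatide will be compared", and these "will be compared at all time-points using repeated measures ANOVA". The next sentence gives the Student t test for continuous variables between the two groups, without restating what each received.

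The End-Points section returns to ticagrelor without eptifibatide. The primary end point compares %IPA "in patients randomized to the loading dose of ticagrelor with loading dose of clopidogrel and 2 boluses of eptifibatide measured at 2 h", and the secondary end points name the same arms. Anticipated Findings follows suit: "we expect that %IPA at 24 h will be higher with ticagrelor than clopidogrel and eptifibatide bolus".

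**The concern.** The ANOVA sentence is the only one that ties a statistical method to %IPA by name. Taken at its word, it compares two oral agents on a shared eptifibatide background. That is a different question from the one the trial poses, which is whether ticagrelor alone does as well as clopidogrel with eptifibatide. An analysis plan that mislabels its main contrast could leave a reader unsure what was tested, and what each arm received also bears on how the bleeding outcomes are read.

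There is a second, smaller point. The comparator's eptifibatide appears as *bolus*, *bolus only* and *2 boluses* in different places, and the available text does not link the three.

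**Working it through.** No formula applies. The documents give no effect size, standard deviation, margin or power calculation, and no %IPA value for clopidogrel plus eptifibatide. The check is to set every statement of this trial's comparison side by side, leaving out statements about the future larger trial.

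| Place | Statements | Eptifibatide with ticagrelor? | Comparator's eptifibatide |
|---|---|---|---|
| Rationale, including Study Hypothesis | 4 | No | bolus |
| Methods | 1 | No, on the natural reading | bolus only |
| Statistical Analysis, opening | 1 | No | 2 boluses |
| Statistical Analysis, ANOVA sentence | 1 | **Yes** | 2 boluses |
| End-Points, primary and secondary | 2 | No | 2 boluses |
| Anticipated Findings, 2 h and 24 h | 2 | No | bolus |

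Total: 4 + 1 + 1 + 1 + 2 + 2 = 11. Eptifibatide is placed in the ticagrelor arm in 1 of 11 and not in 11 − 1 = 10. The comparator wording is *bolus* 4 + 2 = 6 times, *bolus only* once and *2 boluses* 1 + 1 + 2 = 4 times; 6 + 1 + 4 = 11.

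**Is the odd sentence likely to be a slip?** Yes. It disagrees with the opening of its own section and with the end points that follow it. It also drops the loading-dose wording on the ticagrelor side while keeping it on the clopidogrel side, which suggests loose drafting. The 2 h expectation in Anticipated Findings rests on ticagrelor's rapid onset; that reason would hardly be needed if both arms had eptifibatide on board.

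**What would an analyst do with it?** Two arms are randomised. The ANOVA needs a group factor, and the only one available is the randomised allocation. The outcome, time-points, patients and model are the same whether the ticagrelor group is labelled with or without eptifibatide.

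**Does the sentence have to govern the primary end point?** No. That end point is a continuous measure at one time, 2 h, and the t-test sentence can cover it while referring only to the two groups.

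**Do the three comparator wordings conflict?** Not necessarily. The background account of the group's earlier 70-patient study contrasts bolus-only dosing with a bolus plus a 2 h infusion. *Bolus* can therefore describe how the drug is given (no infusion) rather than how many doses. The Methods section also points to Fig. 2 for the design; that figure is not shown in the text available here and may state the regimen.

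**The case for a change.** The best argument for treating this as more than a slip is that the literal reading is not absurd. Both arms of the group's earlier 70-patient study received ticagrelor with eptifibatide, so a ticagrelor-plus-eptifibatide arm is something these investigators have run. In that study, %IPA at 2 h with ADP 5 μM was 100% ± 0.01 on ticagrelor plus eptifibatide bolus, at the ceiling. Whether the ticagrelor arm gets eptifibatide therefore matters a great deal to the meaning of a 2 h result. The schedule in Table 1, as extracted, has no study-drug row to settle it, and correcting one sentence costs almost nothing.

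Part of this stands. The text is inconsistent, the PDF conversion did not cause it, and the arm descriptions must be reconciled. The argument falls short on consequence. What patients receive is set by the randomised treatment, not by a label in the statistics section, so rewording that label cannot alter the data or the contrast. Nor is a reader left guessing about the ticagrelor arm: the hypothesis, the opening of Statistical Analysis and the %IPA end points all describe it without eptifibatide. The earlier study's ceiling value shows why the label matters to a reader, but it comes from patients with NSTEMI, whom this trial excludes, and it implies no bias here.

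**Conclusion.** The inconsistency is genuine but clerical, and no change to the analysis follows. One statement in 11 misdescribes the ticagrelor arm relative to the rest. The effect on the groups compared, the outcome, the model and the result is nil. The comparator wording is an unreconciled description rather than a contradiction.

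This rests on two assumptions: that the analysis compares the two randomised arms, which is the only grouping the design offers, and that treatment was given as the randomised allocation specifies, which the text alone cannot confirm. The arm descriptions in Rationale, Methods, Statistical Analysis, End-Points and Anticipated Findings should be brought into line as ordinary editing. Nothing here says which eptifibatide regimen is right.
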